7.4.3 Hepatotoxicity Stopping and Rechallenge Rules

Refer to [Appendix 7](#) for details regarding drug-induced liver injury (DILI) guidelines, as specified in the *Guidance for Industry Drug-Induced Liver Injury: Premarketing Clinical Evaluation, July 2009*.

7.5 Preparation/Handling/Storage/Accountability

Guidance and information on preparation, handling, storage, accountability, destruction, or return of the investigational product during the study are provided in the IPIM.

7.6 Treatment Compliance

Subjects will receive the SC doses of investigational product at the study centers. The doses will be administered by qualified study personnel for the duration of the study. All efforts should be made to administer investigational product within the defined study windows. In the case of an out of window visit, investigational product can be administered within 1 week of the target visit day (ie, calculated from the day 1 visit). If investigational product cannot be administered within 1 week of the target visit date, the dose is considered missed.

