6.4 Screen Failures

Screen failures are defined as subjects who consent to participate in the clinical study but are not subsequently enrolled in the study. A minimal set of screen failure information will be collected that includes demography, screen failure details, eligibility criteria, medical history, prior therapies, and any serious adverse events.

Individuals who do not meet the criteria for participation in this study (screen failure) will not be rescreened.

7. Treatments

Study treatment is defined as any investigational product(s), non-investigational product(s), placebo, or medical device(s) intended to be administered to a study subject according to the study protocol.

Note that in several countries, investigational product and non-investigational product are referred to as investigational medicinal product and non-investigational medicinal product, respectively.

The Investigational Product Instruction Manual (IPIM), a document external to this protocol, contains detailed information regarding the storage, preparation, destruction, and administration of each treatment shown in [Table 7-1](#) below.

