7.1 Treatment Procedures

7.1.1 Investigational Products

The amount of investigational product, total volume, quantity, dose start date/time, and box number are to be recorded on each subject's CRF.

Table 7-1. Study Treatments

Study Treatment Name	Amgen Investigational Product:^a	Placebo
Dosage Formulation	Each package will contain 3 vials.	Placebo will be presented in identical containers, and stored/packaged the same as tezepelumab.
Unit Dose Strength(s)/ Dosage Level(s) and Dosage Frequency	
Each subject will receive 3 injections per visit.
 
For subjects randomized to 420 mg SC Q2W, 280 mg SC Q2W, and 210 mg SC Q4W: volumes for injections from vials provided will be detailed in the Investigational Product Instruction Manual (IPIM).
 
Subjects randomized to Q4W dosing will receive placebo at intervening visits, such that all subjects receive an injection Q2W.
	
Each subject will receive 3 injections per visit.
 
For subjects randomized to placebo: volumes for injections from vials provided will be detailed in the IPIM.
 
Subjects will receive placebo dosing Q2W.

Route of Administration	SC injection	SC injection
Accountability	The amount of investigational product, total volume, quantity, dose start date/time, and box number of investigational product are to be recorded on each subject's CRF(s).	The amount of investigational product, total volume, quantity, dose start date/time, and box number of investigational product are to be recorded on each subject's CRF(s).
Dosing Instructions	
Investigational product will be administered by qualified study center personnel as the final activity for each study visit. The window for study visits is \pm 3 days.
 
Injection sites are to be rotated.
 
Subjects will be observed for 2 hours post-treatment at the day 1 and week 2 visits. For all other visits where investigational product is administered, subjects will be observed for a period of time at the discretion of the Investigator.
	
Investigational product will be administered by qualified study center personnel as the final activity for each study visit. The window for study visits is \pm 3 days.
 
Injection sites are to be rotated.
 
Subjects will be observed for 2 hours post-treatment at the day 1 and week 2 visits. For all other visits where investigational product is administered, subjects will be observed for a period of time at the discretion of the Investigator.

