7.7 Treatment of Overdose

A dose in excess of 420 mg tezepelumab administered within a 1-week period is considered an overdose. There is currently no specific treatment in the event of overdose of tezepelumab and the effects of overdose of this product are not known. An overdose with associated adverse events is recorded as the adverse event diagnosis/symptoms on the relevant adverse event modules in the Event CRF.

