9.1.2 Treatment Period

Visits will occur per the Schedule of Activities ([Table 2-1](#) and [Table 2-2](#)). On-site study visits may be completed within a window of 3 days. The date of the first dose of tezepelumab or placebo is defined as day 1. All subsequent doses and study visits will be scheduled based on the day 1 date. Administration of tezepelumab or placebo is to occur following completion of all other study activities for each visit.

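### Protocol 7.6 allows a dose 5 to 7 days late to be followed by the next one 4 to 6 days later, an overdose under 7.7 for Q2W dosing, because no minimum interval is stated

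*Protocol*

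**What the plan says.** Four rules bear on the spacing of doses.

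- **Schedule.** Protocol 9.1.2: "The date of the first dose of tezepelumab or placebo is defined as day 1", and "All subsequent doses and study visits will be scheduled based on the day 1 date". A late dose therefore does not move the next target, and Q2W targets stay 14 days apart.
- **Routine window.** The same section: "On-site study visits may be completed within a window of 3 days".
- **Out-of-window dosing.** Protocol 7.6 asks sites to make all efforts to dose in window. It then says that in an out-of-window case "investigational product can be administered within 1 week of the target visit day". The only limit is: "If investigational product cannot be administered within 1 week of the target visit date, the dose is considered missed".
- **Overdose.** Protocol 7.7: "A dose in excess of 420 mg tezepelumab administered within a 1-week period is considered an overdose". It adds that there is no specific treatment and that the effects are not known.

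The dosing text in Protocol 7.1.1, 7.4.2, 7.6 and 9.1.2, the Schedule of Activities footnotes and the SAP contain no minimum interval. Nor do they tell sites to skip or delay the next dose after a late one. Protocol Section 7 refers to the IPIM, which "contains detailed information regarding the storage, preparation, destruction, and administration of each treatment". The IPIM is not among the documents.

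**The concern.** Sections 7.6 and 7.7 are adjacent but not tied together. The first tests each dose only against its own target. The second depends on how close two doses are to each other. A site can keep both doses within their permitted days and still give more than 420 mg in a week.

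Sites are blinded (Protocol 7.3). Two visits may deliver 840 mg, 560 mg, 210 mg or nothing, so a limit in milligrams is hard for a site to apply directly; a limit in days is not.

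At stake is a dosing safety rule, not the efficacy inference. Under Appendix 4, an unintentional overdose is not in itself an adverse event. A symptom-free one would show up only from the dosing record, where "total volume, quantity, dose start date/time, and box number are to be recorded" on the CRF, and so only after the fact.

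**Working it through.** The plan states no dosing-interval figure to reproduce, so this is a direct count.

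**Inputs.** Q2W targets are 14 days apart (Protocol 9.1.2). The routine offset from target is −3 to +3 days (9.1.2, Table 2-1). The out-of-window offset is up to 7 days (7.6). The overdose limit is more than 420 mg in a week (7.7). Target day = week × 7 + 1 (SAP Appendix A).

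**Formula.** With offsets d1 for the earlier dose and d2 for the later, gap = 14 + d2 − d1. A gap under 7 days needs d1 − d2 ≥ 8.

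**Routine schedule.** Both offsets −3 to +3: 49 pairs, minimum gap 14 − 3 − 3 = 8 days. No short gaps.

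**Allowance read as late only** (offsets −3 to +7): 11 × 11 = 121 pairs. Short gaps:

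- d1 = 5 with d2 = −3: gap 6
- d1 = 6 with d2 = −3 or −2: gap 5 or 6
- d1 = 7 with d2 = −3, −2 or −1: gap 4, 5 or 6

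That is 1 + 2 + 3 = 6 pairs, each with only one out-of-window visit. Examples: week 4 on day 29 + 7 = 36 and week 6 on day 43 − 3 = 40 (gap 4); week 16 on day 113 + 7 = 120 and week 18 on day 127 − 3 = 124 (gap 4).

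**Allowance read as early or late** (offsets −7 to +7): 15 × 15 = 225 pairs. Short gaps: 7 + 6 + 5 + 4 + 3 + 2 + 1 = 28, made up of

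- 6 late then in window (the pairs above)
- 6 in window then early
- 16 late then early

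The minimum is 14 − 7 − 7 = 0 days. A further 8 pairs give exactly 7 days.

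**Amount from two doses inside a week**

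- 420 mg Q2W: 420 + 420 = 840 mg
- 280 mg Q2W: 280 + 280 = 560 mg
- Week 16 to 18 switch from 280 mg: 280 + 420 = 700 mg
- Week 16 to 18 switch from 210 mg: 210 + 420 = 630 mg
- Week 16 to 18 switch from placebo: 0 + 420 = 420 mg, not in excess

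**Not affected**

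- Day 1 to week 2: the first dose has offset 0, so the gap is at least 14 − 7 = 7 days.
- Unswitched 210 mg Q4W: active doses are at least 28 − 7 − 7 = 14 days apart.
- Three doses in one week: the minimum span is 28 − 14 = 14 days, so 840 mg is the maximum.

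**Where it can arise.** Dosing every 2 weeks from day 1 to week 50 gives 26 doses and 25 intervals. In the Part A Q2W arms and the Part B active arm, 24 are open to it. Switchers from 210 mg Q4W are open to it from the week 16 to 18 interval, and switchers from placebo from weeks 18 to 20.

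**The case against.** The strongest reply is that a site must follow the whole protocol. Section 7.6 permits and does not require, and 7.7 comes straight after it, so 7.7 can be read as capping what 7.6 allows. That is fair as far as it goes. But 7.7 classifies and records an overdose; it does not tell a site to hold or re-space a dose. Reading it as a limit on single doses only would leave its reference to a 1-week period without a function.

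The IPIM may contain a spacing rule. This stands: the absence is established only for the protocol and SAP. Section 7.6 does not refer to the IPIM for spacing.

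A reader might infer that the protocol plainly allows two doses on the same day. The documents do not support that. Section 7.6 does not say whether its week runs early as well as late, and the sentence on missed doses fits late dosing. All gaps under 4 days, and 22 of the 28 short pairs, depend on the wider reading. Sixteen of the 28 also need two consecutive out-of-window visits in opposite directions.

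A reader might also take 28 of 225 as a frequency. It counts permitted combinations and says nothing about how often they would occur.

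Nor do the documents show harm. Section 3.3 reports no identified risks to date, and the dose justification in 5.4 is redacted, so no exposure margin can be judged either way.

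**Conclusion.** The point holds as a low-severity precaution. On either reading of the 1-week allowance, a single dose 5 to 7 days late can be followed by an in-window dose 4 to 6 days later. In both Q2W regimens, and at the switch from 210 or 280 mg, the total is 560 to 840 mg against a limit of 420 mg. Gaps of 0 to 3 days exist only if early out-of-window dosing is also allowed.

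This assumes whole-day counting, a cumulative reading of 7.7, and no spacing rule in the IPIM. The routine schedule is sound, sites are told to dose in window, and no planned analysis is affected.

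**What to change.** Add to Protocol 7.6, for all arms and including placebo visits so that the blind is kept: *Consecutive investigational product administrations must be at least 7 full days apart; if this cannot be met within 1 week of the later dose's target day, that dose is considered missed.* If the IPIM already has such a rule, a cross-reference in 7.6 is enough.

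The rule requires d2 ≥ d1 − 7. It removes all 28 short pairs and keeps all 49 routine pairs. After a dose 7 days late, the earliest next dose is at offset 0, its exact target day, so the spacing rule alone need not cost a dose. With a gap of exactly 7 days, no period of 7 calendar days contains both doses.

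An 8-day minimum is an optional stricter choice that also removes the 8 boundary pairs. Its drawback is that it bars the target day after a dose 7 days late. For example, a week 14 dose on day 99 + 7 = 106 would bar the week 16 dose on day 113, the target day of the primary endpoint visit.

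The cost is one added sentence and a site memo, with slightly less flexibility for the visit next to an out-of-window dose: after a dose 5, 6 or 7 days late, the next visit loses the first 1, 2 or 3 days of its dosing window. Sample size and analyses do not change.

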7.7 Treatment of Overdose

A dose in excess of 420 mg tezepelumab administered within a 1-week period is considered an overdose. There is currently no specific treatment in the event of overdose of tezepelumab and the effects of overdose of this product are not known. An overdose with associated adverse events is recorded as the adverse event diagnosis/symptoms on the relevant adverse event modules in the Event CRF.

7.8 Prior and Concomitant Treatment

7.8.1 Prior Treatment

Prior therapies that were being taken from 5 years prior to screening through the first dose of investigational product should be collected.

For prior therapies being taken for the disease under study (eg, steroids, topical medications), collect therapy name, indication, dose, unit, frequency, route, start date and stop date. For all other prior therapies, collect therapy name, indication, dose, unit, frequency, route, and start date and stop date.

7.8.2 Concomitant Treatment

Throughout the study, investigators may prescribe any concomitant medications or treatments deemed necessary to provide adequate supportive care except for those listed in [Section 7.1.7](#).

Concomitant therapies are to be collected from the first dose of investigational product through the end of study safety follow-up.

For concomitant therapies being taken for the disease under study (eg, steroids, topical medications) collect therapy name, indication, dose, unit, frequency, route, start date and stop date. For all other concomitant therapies, collect therapy name, indication, dose, unit, frequency, route, start date and stop date.

Allowed concomitant treatments and directions pertaining to rescue therapy are outlined in [Section 7.1.5](#).

8. Discontinuation Criteria

Subjects have the right to withdraw from investigational product and/or other protocol-required therapies, protocol procedures, or the study as a whole at any time and for any reason without prejudice to their future medical care by the physician or at the institution.

The investigator and/or sponsor can decide to withdraw a subject(s) from investigational product, device, and/or other protocol-required therapies, protocol procedures, or the study as a whole at any time prior to study completion for the reasons listed in [Sections 8.1, 8.2.1, and 8.2.2](#).

8.1 Discontinuation of Study Treatment

Subjects (or a legally acceptable representative) can decline to continue receiving investigational product and/or other protocol-required therapies or procedures at any

time during the study but continue participation in the study. If this occurs, the investigator is to discuss with the subject the appropriate processes for discontinuation from investigational product or other protocol-required therapies and must discuss with the subject the possibilities for continuation of the Schedule of Activities (see [Table 2-1](#) and [Table 2-2](#)) including different options of follow-up (eg, in person, by phone/mail, through family/friends, in correspondence/communication with other treating physicians, from the review of medical records) and collection of data, including endpoints, adverse events, disease-related events, and must document this decision in the subject's medical records. Subjects who receive systemic rescue therapies will be discontinued from study treatment but whenever safe and feasible, it is imperative that subjects remain on-study to ensure safety surveillance and/or collection of outcome data. Subjects who have discontinued investigational product and/or other protocol-required therapies or procedures should not be automatically removed from the study. Whenever safe and feasible, it is imperative that subjects remain on-study to ensure safety surveillance and/or collection of outcome data.

Subjects may be eligible for continued treatment with Amgen investigational product(s) and/or other protocol-required therapies by a separate protocol or as provided for by the local country's regulatory mechanism, based on parameters consistent with [Appendix 3](#).

Reasons for removal from protocol-required investigational product(s) or procedural assessments include any of the following:

- Decision by Sponsor
- Lost to follow-up
- Death
- Ineligibility determined
- Protocol deviation
- Non-compliance
- Adverse event
- Subject request
- Pregnancy

8.2 Discontinuation From the Study

Withdrawal of consent for a study means that the subject does not wish to receive further protocol-required therapies or procedures, and the subject does not wish to or is unable to continue further study participation. Subject data up to withdrawal of consent will be included in the analysis of the study, and where permitted, publicly available data

can be included after withdrawal of consent. The investigator is to discuss with the subject appropriate procedures for withdrawal from the study, and must document the subject's decision to withdraw in the subject's medical records.

If a subject withdraws from the study, he/she may request destruction of any samples taken and not tested, and the investigator must notify Amgen accordingly (see [Appendix 6](#) for further details). Refer to the Schedule of Activities for data to be collected at the time of study discontinuation and follow-up and for any further evaluations that need to be completed.

8.2.1 Reasons for Removal From Washout, Run-in, or Invasive Procedures

Not applicable to this study.

8.2.2 Reasons for Removal From Study

Reasons for removal of a subject from the study are:

- Decision by sponsor
- Withdrawal of consent from study
- Death
- Lost to follow-up

8.3 Lost to Follow-up

A subject will be considered lost to follow-up if he or she repeatedly fails to return for scheduled visits and is unable to be contacted by the study center.

The following actions must be taken if a subject fails to return to the clinic for a required study visit:

- The study center must attempt to contact the subject and reschedule the missed visit as soon as possible and counsel the subject on the importance of maintaining the assigned visit schedule and ascertain whether or not the subject wishes to and/or is able to continue in the study.
- In cases in which the subject is deemed lost to follow-up, the investigator or designee must make every effort to regain contact with the subject (where possible, 3 telephone calls and, if necessary, a certified letter to the subject's last known mailing address or local equivalent methods). These contact attempts are to be documented in the subject's medical record.
- If the subject continues to be unreachable, he/she will be considered to have withdrawn from the study with a primary reason of lost to follow-up.
- For subjects who are lost to follow-up, the investigator can search publicly available records [where permitted]) to ascertain survival status. This ensures that the data set(s) produced as an outcome of the study is/are as comprehensive as possible.

9. Study Assessments and Procedures

Study procedures and their time points are summarized in the Schedule of Activities (see [Table 2-1](#) and [Table 2-2](#)).

As protocol waivers or exemptions are not allowed if an enrolled subject is subsequently determined to be ineligible for the study, this must be discussed with the sponsor immediately upon occurrence or awareness to determine if the subject is to continue or discontinue study treatment.

Adherence to the study design requirements, including those specified in the Schedule of Activities, is essential and required for study conduct.

9.1 General Study Periods

9.1.1 Screening, Enrollment, and Randomization

Informed consent must be obtained before completing any screening procedure or discontinuation of standard therapy for any disallowed therapy. After the subject has signed the informed consent form, the study center will register the subject in the IVRS/IWRS and screen the subject in order to assess eligibility for participation. The screening window for this study is up to 28 days (+ 7 days).

All screening evaluations must be completed and reviewed to confirm that potential subjects meet all eligibility criteria. The investigator will maintain a screening log to record details of all subjects screened and to confirm eligibility or record reasons for screening failure, as applicable.

If a subject has not met all eligibility criteria at the end of the screening period, the subject will be registered as a screen fail. Screen fail subjects are not eligible for rescreening.

9.1.2 Treatment Period

Visits will occur per the Schedule of Activities ([Table 2-1](#) and [Table 2-2](#)). On-site study visits may be completed within a window of 3 days. The date of the first dose of tezepelumab or placebo is defined as day 1. All subsequent doses and study visits will be scheduled based on the day 1 date. Administration of tezepelumab or placebo is to occur following completion of all other study activities for each visit.

9.1.3 Safety Follow-up

A safety follow-up visit will be conducted 20 weeks after the final dose of study drug (18 weeks after the EOT visit). All subjects who terminate the study early will complete an early termination visit consisting of all assessments included in the EOT (week 52)

visit and these subjects will complete a safety follow-up visit occur 18 weeks after the EOT visit.

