^m Administration of study drug is the final activity performed at a visit. Subjects randomized to Q4W dosing will receive placebo at the visits between dosing with tezepelumab. Subjects will be observed for 2 hours post-treatment at the day 1 and week 2 visits. For all other visits where investigational product is administered, subjects will be observed for a period of time at the discretion of the Investigator.

ⁿ All subjects will receive a 420 mg SC dose of either study drug or placebo as their first dose.

^o Only certain inclusion criteria specified in the protocol will be re-evaluated at the day 1 visit. These criteria will be evaluated prior to any other day 1 study activities and are required to be met for dosing with investigational product.

^p All subjects who terminate the study early will complete an early termination visit consisting of all assessments included in the EOT (week 52) visit. In addition, a safety follow-up visit will occur 18 weeks after the EOT visit.

Table 2-2. Schedule of Activities for Part A and Part B (Week 26 Through End of Study)

	Treatment Period (52 weeks) ^a														EOT ^a /ET ^l	EOS ^a		Unscheduled
	Wk 26	Wk 28	Wk 30	Wk 32	Wk 34	Wk 36	Wk 38	Wk 40	Wk 42	Wk 44	Wk 46	Wk 48	Wk 50	Wk 52	Wk 58	Wk 70		
GENERAL AND SAFETY ASSESSMENTS																		
Physical examination															X	X	X	X
12-lead ECG ^b																	X	X
Vital signs ^c	X	X	X	X	X	X	X	X	X	X	X	X	X	X	X	X	X	X
Adverse events	X	X	X	X	X	X	X	X	X	X	X	X	X	X	X	X	X	X
Serious adverse events	X	X	X	X	X	X	X	X	X	X	X	X	X	X	X	X	X	X
Disease-related events	X	X	X	X	X	X	X	X	X	X	X	X	X	X	X	X	X	X
Concomitant therapies review	X	X	X	X	X	X	X	X	X	X	X	X	X	X	X	X	X	X
LABORATORY ASSESSMENTS																		
Urine pregnancy test ^d		X		X		X		X		X		X		X		X		X
Coagulation													X	X				X
Hematology						X						X		X	X	X		X
Chemistry						X						X		X	X	X		X
Urinalysis (dipstick) ^e						X						X		X	X	X		
Anti-tezepelumab-antibody						X						X					X	X
Serum immunoglobulins ^f					X							X		X				X
PPD or Quantiferon GOLD														X				
STUDY-SPECIFIC ASSESSMENTS																		
Electronic diary ^g	Completed in the morning at home on eDiary																X	X
Assessment of EASI and IGA						X							X	X	X		X	
SCORAD						X							X	X	X			
EQ-5D-3L, POEM, DLQI, PGI-S						X							X	X	X			
Tracking of TCS use (Part B subjects only)	X	X	X	X	X	X	X	X	X	X	X	X	X	X	X	X	X	X

Footnotes defined on last page of the table

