Table 2-2. Schedule of Activities for Part A and Part B (Week 26 Through End of Study)

	Treatment Period (52 weeks) ^a													EOT ^a /ET ^l		EOS ^a	Unscheduled
	Wk 26	Wk 28	Wk 30	Wk 32	Wk 34	Wk 36	Wk 38	Wk 40	Wk 42	Wk 44	Wk 46	Wk 48	Wk 50	Wk 52	Wk 58	Wk 70	
PHARMACOKINETIC ASSESSMENTS																	
PK sampling ^l				X				X				X	X	X	X	X	
STUDY TREATMENT																	
Administration of tezepelumab or placebo ^k	X	X	X	X	X	X	X	X	X	X	X	X	X				

Page 2 of 2

DLQI = Dermatology Quality of Life Index; EASI = Eczema Area and Severity Index;
 ECG = electrocardiogram; Echo = echocardiogram; eCRF = electronic case report form; EOS = end of study; EOT = end of treatment; EQ-5D-3L = EuroQOL quality of life 5-dimensions 3-level version; ET = early termination; Ig = immunoglobulin; IGA = Investigator's Global Assessment; NRS = numeric rating scale; PGI-S = Patient's Global Impression of Severity; PK = pharmacokinetics; POEM = Patient Oriented Eczema Measure; PPD = purified protein derivate; SCORAD = Scoring Atopic Dermatitis; TCS = topical corticosteroids; Wk = Week

^a The window for visits is ± 3 days.

^b ECG must be collected prior to any blood draws.

^c Vital signs will be taken pre-dose prior to administration of investigational product. Subjects will be observed for 2 hours post-treatment at the day 1 and week 2 visits. For all other visits where investigational product is administered, subjects will be observed for a period of time at the discretion of the Investigator.

^d Pregnancy testing applies to females of childbearing potential only, as defined in the protocol. The pregnancy test at screening must be a serum pregnancy test. All other scheduled pregnancy tests will be urine tests. Additional on-treatment pregnancy testing may be performed at the investigator's discretion if there is suspicion that a female subject is pregnant or per local laws and regulations. If a urine pregnancy test is positive, a confirmatory serum pregnancy test will be performed by the study center and entered into the eCRF.

^e Urinalysis analyzed centrally only if dipstick locally is positive.

^f This includes total serum IgE, IgA, IgG, and IgM. All immunoglobulin results will be redacted from laboratory reports.

^g The eDiary includes Pruritus NRS.

^j PK samples at day 1 and weeks 2, 4, 12, 16, 24, 32, 40, 48, and 50 should be collected before dosing with investigational product (trough).

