^k Administration of study drug is the final activity performed at a visit. Subjects randomized to Q4W dosing will receive placebo at the visits between dosing with tezepelumab. Subjects will be observed for 2 hours post-treatment at the day 1 and week 2 visits. For all other visits where investigational product is administered, subjects will be observed for a period of time at the discretion of the Investigator.

^l All subjects who terminate the study early will complete an early termination visit consisting of all assessments included in the EOT (week 52) visit. In addition, a safety follow-up visit will occur 18 weeks after the EOT visit.

3. Introduction

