5.3.2 Study Duration for Subjects

In Part A, for an individual subject, the length of participation includes a screening period of up to 28 days, a double-blind treatment period of 52 weeks, and a safety follow-up that occurs for 20 weeks after the final dose of study drug (18 weeks after the end of treatment [EOT] visit).

In Part B, for an individual subject, the length of participation includes a screening period of up to 28 days, a double-blind treatment period of 52 weeks, and a safety follow-up that occurs for 20 weeks after the final dose of study drug (18 weeks after the EOT visit).

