9.1.4 End of Study

The EOS visit will occur 18 weeks after the EOT visit (20 weeks after the final dose of study drug) and is the same as the safety follow-up visit.

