Other minor, protocol clarifications and inconsistencies were updated during this amendment.

Approved

Amendment 1

Protocol Title: A Dose-Ranging, Double-Blind, Placebo Controlled Study to Evaluate the Safety and Efficacy of Tezepelumab Alone or Combined With Topical Corticosteroids in Moderate-to-Severe Atopic Dermatitis

Amgen Protocol Number (Tezepelumab) 20170755

Amendment Date: 20 November 2018

Rationale:

The main purpose of this protocol amendment is to address regulatory questions from EU VHP EU VHP-No: VHP1358 (VHP2018120) - RTQ submitted 06 Nov 2018 and to correct minor editorial changes and errors.

The major changes to the protocol are outlined below:

- Updated the safety follow-up period in response to RTQ Amended protocol from VHP to address GNA #55 by extending follow up period to 20 weeks after last dose.
- Added additional descriptive statistics for continuous endpoints in response to RTQ Amended protocol from VHP to address GNA #38.
- Added PPD or Quantiferon GOLD testing at screening and EOT/ET visits as requested by VHP RTQ #5, 19, and 20.
- Updated inclusion criterion 107 as a recommendation from study sites and KOLs as restriction of moisturizer type would impact recruitment and not influence efficacy.
- Updated exclusion criterion 215 in response to RTQ Amended protocol from VHP to address GNA #23.
- Removed language regarding receiving treatment with systemic corticosteroids or nonsteroidal systemic immunosuppressive drugs after week 16 in response to RTQ Amended protocol from VHP to address GNA #26, 45, 52, 53.
- Updated interim analysis guidelines in response to RTQ Amended protocol from VHP to address GNA #54.
- Updated contraception guidance in response to RTQ Amended protocol from VHP to address GNA #46.

Approved

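### For early terminators the follow-up visit is tied only to 18 weeks after EOT, which can fall up to 13 days (nominal) short of the stated 20 weeks after the last dose

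*Protocol*

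**What the plan says.** The protocol states the follow-up interval from two starting points.

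- **From the last dose.** Section 9.1.3 opens with "A safety follow-up visit will be conducted 20 weeks after the final dose of study drug" and gives 18 weeks after EOT in brackets as the equivalent. Section 5.3.2 describes "a safety follow-up that occurs for 20 weeks after the final dose of study drug" with the same bracket, and 9.1.4 pairs the two intervals again for the EOS visit. The rationale for Amendment 1, used here only to show the aim, speaks of "extending follow up period to 20 weeks after last dose".
- **From EOT alone.** For subjects who terminate early, the last sentence of 9.1.3 says that "these subjects will complete a safety follow-up visit occur 18 weeks after the EOT visit". Footnote p of Table 2-1 and footnote l of Table 2-2 agree: "In addition, a safety follow-up visit will occur 18 weeks after the EOT visit". None of these three places mentions the last dose.

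The reporting periods also differ. Section 9.2.3.1.1.3 takes serious adverse events to 20 weeks after the last dose. Section 9.2.3.1 ends adverse event collection at the follow-up visit or at 20 weeks after the last dose, without saying which governs. SAP 5.1 closes the TEAE window at the End of Study Date. SAP 5.2 defines that date as completion of safety follow-up or, failing that, the ET visit.

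**The concern.** The 18-week and 20-week intervals are interchangeable only if EOT comes exactly two weeks after the last dose. The visit schedule guarantees that, on nominal dates, for subjects who complete treatment. It does not for someone whose ET visit is held partway through a dosing cycle. For that person the two rules give different dates, and the sentence written specifically for them gives the earlier one.

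At stake is the last stretch of safety observation. If the follow-up visit comes early, the subject's End of Study Date comes early too. An event starting after that visit but within 20 weeks of the last dose then falls outside the SAP's TEAE definition and its Day 1 to EOS tables (SAP 9.6). A serious event in that gap would be reportable under the protocol and still absent from those tables.

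**Working it through.** **Inputs**

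- Target days follow SAP Appendix A: week × 7 + 1.
- Last scheduled dose: week 50 (Table 2-2, dosing row). EOT: week 52. EOS: week 70.
- 20 weeks = 140 days; 18 weeks = 126 days.
- EOT for an early terminator is read as the ET visit. This is an inference. Table 2-2 has one shared EOT/ET column, and Appendix 1 defines end of treatment by the individual subject's last treatment-phase assessment.
- "Administration of study drug is the final activity performed at a visit" (footnotes to both schedule tables), and Table 2-2 shows no dose in the EOT/ET column. An ET visit is therefore taken to fall at least 1 day after the last dose.
- "The window for visits is ± 3 days" (footnotes to both tables). The window is left out of the nominal figures.

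**The plan's own equivalence, for completers**

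- Last dose: 50 × 7 + 1 = day 351. EOT: 52 × 7 + 1 = day 365. EOS: 70 × 7 + 1 = day 491.
- EOT − last dose = 365 − 351 = 14 days.
- EOS − EOT = 491 − 365 = 126 days = 18 weeks.
- EOS − last dose = 491 − 351 = 140 days = 20 weeks.

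The stated pairing reproduces exactly.

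**Early terminators**

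Let L be the days from last dose to ET visit. Follow-up falls at 126 + L days after the last dose, so the shortfall is max(0, 140 − (126 + L)) = max(0, 14 − L).

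| L (days) | Follow-up, days after last dose | Days short of 140 |
|---|---|---|
| 1 | 127 | 13 |
| 3 | 129 | 11 |
| 7 | 133 | 7 |
| 10 | 136 | 4 |
| 13 | 139 | 1 |
| 14 or more | 140 or more | 0 |

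**Plausible range**

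The documents give no distribution of L. Two assumptions show the range:

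- ET held at the next scheduled visit within ±3 days (L = 11 to 17): the shortfall is 3, 2, 1, then 0 from L = 14 onward.
- ET days spread evenly over the dosing cycle (L = 1 to 14): mean shortfall = (13 + 12 + … + 0)/14 = 91/14 = 6.5 days.

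The shortest nominal interval, 127 days, still exceeds the 16-week (112-day) pregnancy reporting period in 9.2.3.1.6.

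**The case against.** The best reply is that the 20-week rule is already general. The opening of 9.1.3 is not limited to completers, and 5.3.2 states the interval for each individual subject. On this view the sentence on early terminators is shorthand, and a site reading the whole section would find the dose-based interval just above it. That makes the problem one of drafting and not of design. It does not remove the conflict, because the footnotes to the schedule tables carry only the 18-week rule.

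Four further points bear on weight.

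- **Few subjects are exposed.** Under 8.1, subjects who only stop drug are meant to remain on study; if they leave later, L will usually be 14 or more. Section 8.2.2 lists four reasons for removal. Death and loss to follow-up produce no visit, and withdrawal of consent (8.2) ends procedures. What remains is mainly sponsor decision, including termination of both parts after a futile interim result (5.1). That is an inference, and no count is available.
- **Thirteen days is a corner case.** It needs an ET visit the day after a dose.
- **The protocol already tolerates similar variation.** A completer dosed 7 days late at week 50 (allowed by 7.6; day 358) and seen 3 days early at EOS (day 488) has 488 − 358 = 130 days, 10 short.
- **Serious events are covered.** Their reporting does not depend on the visit date.

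All four stand, and they keep the point small. They do not make the two rules agree.

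A reader might go further and infer that early terminators have only an 18-week safety period, or that serious events go unreported. The documents do not support this: 20 weeks is the interval stated in 5.3.2, 9.1.3 and 9.1.4, and 9.2.3.1.1.3 applies it to serious events whenever the visit takes place.

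**Conclusion.** The text is wrong as written, with small reach. For subjects who terminate early, the visit rule in the last sentence of 9.1.3 and in footnotes p and l conflicts with the protocol's own 20-week interval whenever ET is fewer than 14 days after the last dose. The shortfall is 14 − L days: at most 13 on nominal dates, and 0 to 3 if ET is held at the next scheduled visit within ±3 days.

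This rests on two readings: that EOT means the ET visit for these subjects, and that ET is at least 1 day after the last dose. The documents do not expressly exclude an ET visit on a dosing day, which would give 14 days. If EOT meant the literal week 52 visit there would be no shortfall, but a subject who has left early has no such visit.

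The consequence is limited to when an affected subject is seen and when that subject's TEAE window closes. It would be tempting to conclude that the safety tables are materially incomplete. The documents give neither the number of affected subjects nor any sign that the missing days matter clinically, so no change to an efficacy result or an overall safety conclusion is shown.

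**What to change.** - **Protocol 9.1.3 and footnotes p and l.** For early terminators, keep 18 weeks after the ET visit and add that the follow-up visit is to be no earlier than 20 weeks after the last dose of investigational product. The nominal visit then falls at max(126 + L, 140) days, so the shortfall is zero for every L. The clause should be applied as a floor: if the ±3-day window could still bring the visit forward, up to 3 days would remain.
- **Protocol 9.2.3.1.** After the two alternative end points for adverse event collection, add that the later one applies. Section 9.2.3.1.6 already uses that construction for pregnancies.

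The cost is a few words, and the follow-up visits of a few early terminators move later by at most 13 days.

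Completers' visit windows and the SAP's Week 70 upper bound (day 494) can stay as they are. That bound closes five windows in SAP Appendix A (vital signs; EASI and IGA; pregnancy tests; hematology, chemistry and urinalysis; antibodies). Those windows assign measurements to visits and do not define TEAEs, so moving the bound would not address this point.

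One gap remains. For a subject who misses follow-up, the SAP's End of Study Date is still the ET visit.
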